8.3.1 Exposures

Empagliflozin (current ATC code A10BK03, previous ATC code A10BX12) is the exposure of interest, free or fixed-dose combination with metformin (ATC code: A10BD20).

The DPP-4 inhibitor comparator exposure group will consist of the following drugs, free or fixed-dose combination with metformin (See [Section 8.1](#) and [Annex 4](#)).

- Alogliptin
- Linagliptin
- Saxagliptin
- Sitagliptin
- Vildagliptin

If additional DPP-4 inhibitors are introduced in any of the study countries during the study period, they will also be considered to be members of the corresponding comparator group. Note that use of any of these index drugs prior to index date is an exclusion criterion.

Information on whether patients received prior oral glucose lowering therapy or if they were “added on” or “switched to” empagliflozin, or a DPP-4 inhibitor at the time of inclusion in the study will be collected. Patients will be classified according to their treatment complexity as receiving monotherapy, dual combination therapy, or triple combination therapy and according to use of metformin combination therapy (fixed-dose or free combination). (See Section 8.1)

The primary definition of exposure, i.e., as-treated analysis (AT), is defined as an ongoing exposure (free or fixed-dose combination with drugs other than DPP-4 inhibitors and SGLT-2 inhibitors) to one of the following two index drugs or drug groups: empagliflozin or DPP-4 inhibitors ([Table 3](#), Annex 4). Exposure is defined as use of these drugs during the study period starting from 6 months after the index date (see [Sections 8.2.3](#) and [8.3.5](#))

As a typical prescription length is one month in the UK and three months in Sweden and Finland, multiple prescriptions are required for a patient to have continuous ongoing treatment at 6 months after index date. Therefore, patients with only one prescription are unlikely to contribute to the AT analysis.

Secondary definitions of exposure include cumulative dosage of empagliflozin use, daily dosage of empagliflozin prescribed per use (10mg vs 25mg), and time since first dose of empagliflozin ([Table 3](#), Annex 4).

Sensitivity analyses of exposure include intention-to-treat (ITT) analyses.

Table 3

Exposure definitions for primary and secondary analyses

Exposure definition	Description	Time-dependent or Fixed at index date

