Year	Study drug group	Finland	Sweden	CPRD GOLD	CPRD Aurum ⁴	Pooled
	Other SGLT-2 inhibitors	8,049	7,317	11,211	25,277	51,854

1 Observed number of patients.

2 Observed number of patients until 30th June for Sweden and Finland and until 31st December for UK CPRD GOLD, taking into account the extension of the study period to the end of 2021 for UK CPRD.

3 Expected number of patients (arithmetic growth assumption given observed numbers in previous years) between 1st January and 30th June, taking into account the 6 months minimum follow-up.

4 Only aggregate level data up (2014-2020) of was available for CPRD Aurum. Patient numbers were extrapolated based on assumptions derived from CPRD GOLD data, taking into account the extension of the study period to the end of 2021
DPP-4=dipeptidyl peptidase-4 inhibitors; SGLT-2=sodium glucose co-transporter-2 inhibitors; UK=the United Kingdom

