5.1.2. INDEX DATE

The index date is defined as the date of first dispensation/prescription of empagliflozin or of a DPP-4 inhibitor during the study period (from 1st August, 2014 until 31st December, 2020 – 2021 for UK-CPRD).

[figure not shown]

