5.1.3. EXPOSURE TIME

Time at risk will start on index date and continue until first treatment discontinuation (see definition in Section 5.1.6). Continuous exposure will be defined as successive exposure periods for the study drugs separated by gaps of 30 days at most. Duration of exposure

Proprietary confidential information © 2024 Boehringer Ingelheim International GmbH or one or more of its affiliated companies

episodes for individual prescriptions of study drugs will be derived based on package size, unit strength and daily dose.

To account for an empirical induction/promotion period of cancer, a latency period of 6 months (180 days) after the index date is applied. Patients with less than 6 months (180 days) of follow-up time will be excluded. In addition, patients with any diagnosis of any cancer within the latency period will be excluded. In a sensitivity analysis, the latency period will be extended to 12 months (365 days).

* Other drugs: a prescription of another drug (empagliflozin, a DPP-4 inhibitor, or a SGLT-2 inhibitor) other than index drug

Figure 1 Definition of continuous exposure period of index drug

For the primary AT analyses, the time at risk will begin after the latency period and end at urinary tract (bladder, renal or other) cancer or at any of the censoring events (listed in Table 4), whichever occurs first. In addition, treatment discontinuation of the index drug (defined in Section 5.1.6) is an additional censoring variable.

For the sensitivity ITT analyses, the time at risk will begin after the latency period and end at urinary tract (bladder, renal or other) cancer or any of the censoring events excluding treatment discontinuation of the index drug.

Patients with censored time at risk will not be able to re-enter the study cohort at a later time point. The time at risk will not be censored if oral or injectable glucose-lowering drugs other than the index drugs and SGLT-2 inhibitors are prescribed in addition to empagliflozin or a DPP-4 inhibitor after the index date.

Proprietary confidential information © 2024 Boehringer Ingelheim International GmbH or one or more of its affiliated companies

Table 4 Censoring events.

Censoring event	Definition	Data source
All-cause mortality	Censoring of follow-up time occurs at the date of death regardless of the cause. Applied in all analyses.	UK: CPRD-GOLD and Aurum Sweden: Cause of death register Finland: Cause of death register

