5.1.6. Definition of continuous treatment and discontinuation

Continuous treatment

Continuous treatment is defined as having consecutive treatment episodes separated by a grace period of 30 days (Figure 1). In a sensitivity analysis, the grace period is extended to 90 days.

In case of overlaps between treatment episodes (i.e., a new prescription/dispensation during an ongoing exposure period), the overlapping days are added to the end of the following treatment episode, resulting in a longer treatment episode to take into account possible stockpiling.

Treatment discontinuation

Treatment discontinuation (see Table 4) is defined either by

- The start of a new prescription of any new drug from the following drug groups: empagliflozin, DPP-4 inhibitors, or SGLT-2 inhibitors), or of a fixed-dose combination of a SGLT-2 inhibitor with a DPP-4 inhibitor (identified from the ATC class A10BD)
- The end date of the first continuous exposure period of the index drug (stop date) plus a 3-month (90 days) period following it.

The discontinuation date is defined as the stop date/start date of a new drug plus 90 days.

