6.7.2. Comparative analysis

Hazard ratios (HRs) for the outcomes defined in Table 8 will be estimated for PS matched cohorts using Cox's PH model with time-varying covariates, if model pre-requisites are fulfilled. HRs will be presented along with 95% CIs. Proportional hazards assumptions for time-fixed exposure variables will be assessed for each model by plotting scaled Schoenfeld residuals.

The comparative analyses will be performed separately for the matched full cohort and matched metformin-user cohort.

Crude model

Crude HRs are calculated using a Cox PH model with as-treated exposure (as defined in Section 5.1.7) as the only included variable.

HRs estimated using the crude model will be presented along with 95% CIs. A table template for the result is given in Table 23. Analysis will be performed separately for each country.

Crude HRs with 95% CIs will be collected from all study countries to carry out meta-analyses as described in Section 6.7.3.2. Results will be reported as in Figure 8.

Base model

Based on the crude model, the base model will be further adjusted with the unbalanced covariates at index date (standard difference $\geq 10\%$) among the variables included in the propensity score model (Section 6.6). The inclusion of adjusting variables will be considered based on data availability as described in Section 10.

HRs estimated using the base model will be presented along with 95% CIs. A table template for the result is given in Table 24. Analysis will be performed separately for each country. HRs with 95% CIs estimated using base model will be collected from all study countries to carry out meta-analyses as described in Section 6.7.3.2. Results will be reported as in Figure 8.

Adjusted model

The base model will be further adjusted with selected time-dependent variables. The following time-dependent variables will be initially considered for inclusion (as detailed in Section 9) in the adjusted Cox's PH model:

- HbA1c value (as defined in Table 11)
- Kidney or genitourinary stones (as defined in Table 13)
- UTI or pyelonephritis (as defined in Table 13)
- Ever exposed to insulin (as defined in Table 14)
- Ever exposed to metformin (as defined in Table 14)

Proprietary confidential information © 2024 Boehringer Ingelheim International GmbH or one or more of its affiliated companies

- Ever exposed to other glucose lowering medication (as defined in Table 14)
- Ever exposed to GLP-1 drugs (as defined in Table 14)

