Annex III

Tables and figures templates

Abbreviations: DPP-4, dipeptidyl peptidase-4; T2DM, Type 2 diabetes mellitus.

Definitions: Index date, the date of first purchase/prescription of empagliflozin or DPP-4 between August 1, 2014 and June 30, 2020.

Proprietary confidential information © 2024 Boehringer Ingelheim International GmbH or one or more of its affiliated companies

Table 17 Patients baseline characteristics in each of the study groups and in the total study population in [Study country].

	Empagliflozin at index date	DPP-4 inhibitors at index date	[Country] Study population (Total)
	N	N	
Age at index (years)			
18-49	N (x.xx%)	N (x.xx%)	N (x.xx%)
50-64	N (x.xx%)	N (x.xx%)	N (x.xx%)
65-69	N (x.xx%)	N (x.xx%)	N (x.xx%)
70-74	N (x.xx%)	N (x.xx%)	N (x.xx%)
75-79	N (x.xx%)	N (x.xx%)	N (x.xx%)
80-84	N (x.xx%)	N (x.xx%)	N (x.xx%)
85 and over	N (x.xx%)	N (x.xx%)	N (x.xx%)
Range (min,max)	(min, max)	(min, max)	(min, max)
mean (± sd)	mean (± sd)	mean (± sd)	mean (± sd)
median (Q1,Q3)	median (Q1,Q3)	median (Q1,Q3)	median (Q1,Q3)
Sex			
Male	N (x.xx%)	N (x.xx%)	N (x.xx%)
Female	N (x.xx%)	N (x.xx%)	N (x.xx%)
Highest level of education			
Compulsory	N (x.xx%)	N (x.xx%)	N (x.xx%)
Upper secondary	N (x.xx%)	N (x.xx%)	N (x.xx%)
Post secondary	N (x.xx%)	N (x.xx%)	N (x.xx%)
Disposable income, Individual			
< Q1	N (x.xx%)	N (x.xx%)	N (x.xx%)

Proprietary confidential information © 2024 Boehringer Ingelheim International GmbH or one or more of its affiliated companies

	Empagliflozin at index date	DPP-4 inhibitors at index date	[Country] Study population (Total)
	N	N	
Q1 – Q2	N (x.xx%)	N (x.xx%)	N (x.xx%)
Q2 – Q3	N (x.xx%)	N (x.xx%)	N (x.xx%)
≥ Q3	N (x.xx%)	N (x.xx%)	N (x.xx%)
Range (min,max)	(min, max)	(min, max)	(min, max)
mean (± sd)	mean (± sd)	mean (± sd)	mean (± sd)
median (Q1,Q3)	median (Q1,Q3)	median (Q1,Q3)	median (Q1,Q3)
Disposable income, family			
< Q1	N (x.xx%)	N (x.xx%)	N (x.xx%)
Q1 – Q2	N (x.xx%)	N (x.xx%)	N (x.xx%)
Q2 – Q3	N (x.xx%)	N (x.xx%)	N (x.xx%)
≥ Q3	N (x.xx%)	N (x.xx%)	N (x.xx%)
Range (min,max)	(min, max)	(min, max)	(min, max)
mean (± sd)	mean (± sd)	mean (± sd)	mean (± sd)
median (Q1,Q3)	median (Q1,Q3)	median (Q1,Q3)	median (Q1,Q3)
Marital status			
Registered partnership (incl. married)	N (x.xx%)	N (x.xx%)	N (x.xx%)
Widowed	N (x.xx%)	N (x.xx%)	N (x.xx%)
Separated	N (x.xx%)	N (x.xx%)	N (x.xx%)
Single	N (x.xx%)	N (x.xx%)	N (x.xx%)
Calendar year of index date			
2014	N (x.xx%)	N (x.xx%)	N (x.xx%)
2015	N (x.xx%)	N (x.xx%)	N (x.xx%)

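### The 180-day follow-up rule has no stated place in cohort building or matching, and balance is judged in index-date users rather than in the patients analysed

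*SAP*

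**What the plan says.** SAP 5.1.3 sets the lag, "a latency period of 6 months (180 days) after the index date is applied", and adds the exclusion "Patients with less than 6 months (180 days) of follow-up time will be excluded". Protocol 8.3.5 has the same rule. Neither document says whether the exclusion comes before or after matching.

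The steps that build the cohort do not mention it:
- SAP Tables 2 and 3 list criteria assessed at or before index, with no 180-day condition.
- SAP 6.1 counts the total study population after those criteria only.
- SAP 6.4 and 6.5.2 match initiators at index date, within 90 days either side and without replacement. The caliper is calibrated so that 99% of empagliflozin initiators find a match.

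The index window differs by place. SAP 5.1.2 runs it "from 1st August, 2014 until 31st December, 2020 – 2021 for UK-CPRD", and SAP 4.2.2 and Table 2 agree. The index-date definition in SAP Annex III reads "between August 1, 2014 and June 30, 2020", with no UK exception. Protocol Table 6 stops at 30 June 2020 for Sweden and Finland, and its 2021 CPRD GOLD row covers initiators "between 1st January and 30th June, taking into account the 6 months minimum follow-up".

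On balance, SAP 6.6.2 compares index-date users before and after matching against a 10% standardized difference. SAP 6.7.2 then says that "the base model will be further adjusted with the unbalanced covariates at index date". SAP 6.3 describes study entry as resting on information available up to index.

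**The concern.** There are two separate issues.

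**Late initiators.** A patient who starts less than 180 days before the end of data cannot contribute. If such patients stay in the matching pool, they shape the propensity model and the caliper, and they can use up comparators in a period when comparators are scarce. In January–June 2020, Table 6 shows 5,806 empagliflozin against 4,688 DPP-4 initiators in Sweden, and 2,777 against 2,215 in Finland. With two index windows in the SAP, two programmers could build different cohorts.

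**Early stoppers.** As-treated patients enter the analysis only if they are still under follow-up at day 180. If early stopping differs between arms and is linked to a risk factor, the arms analysed can differ although the index-date table shows balance. The base model would then omit that covariate.

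**Working it through.** **1. The plan's own figure.** Table 7 gives Swedish power of 85.1% for urinary tract cancer at HR 1.5. Inputs: N = 32,334, follow-up 2.2 years, rate 164.5 per 100,000, ratio 1:1; two-sided 5% is assumed. With the half-year lag deducted, events = 32,334 × 1.7 × 0.001645 × (1.5 + 1) = 226. Freedman's formula gives Φ(√226 × 0.5/2.5 − 1.96) = 85.2%. Without the deduction it is 92.8%. The power calculation therefore deducts the lag, and Swedish empagliflozin person-time is 32,334 × 1.7 ≈ 54,970 years.

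**2. Last useful index date.** 31 December minus 180 days is 4 July, in both 2020 and 2021.

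**3. Initiators with no possible follow-up.** Table 6 has no July–December 2020 counts for Sweden or Finland. Assuming they equal January–June:
- Sweden: 5,806 / (32,334 + 5,806) = 15.2%
- Finland: 2,777 / (18,269 + 2,777) = 13.2%

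**4. Effect on matching and person-time.** An idealised first matching round was simulated from the Table 6 counts (uniform dates, no caliper limit, no exact metformin matching, second half of 2020 equal to the first). The share of January–June 2020 empagliflozin initiators who obtain a comparator able to contribute is 80% in Sweden and 81% in Finland without a cap, and 93% and 94% with one. A repeat gave 81% to 92% and 83% to 93%.

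These patients add little time. Starting evenly between 1 January and 30 June, they have between 185 and 4 days left after the lag, a mean of about 0.26 years. In Sweden, 5,806 × 0.26 ≈ 1,510 years, or 1,510 / 54,970 = 2.7% of the total. A 13-point change in usable comparators touches 0.13 × 2.7% ≈ 0.4%.

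**5. What as-treated entry requires.** SAP 5.1.6: "The discontinuation date is defined as the stop date/start date of a new drug plus 90 days". Protocol 8.3.1: "As a typical prescription length is one month in the UK and three months in Sweden and Finland". A single 30-day supply is censored at day 30 + 90 = 120. A single 90-day supply is censored at day 90 + 90 = 180. Neither gives time at risk after the lag, so more than 90 days of continuous supply is needed.

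**6. Why the set checked is not the set analysed.** SAP 6.5.1 creates two matched cohorts per country, full and metformin-user. SAP Table 16 uses matched cohorts for the as-treated, ITT and 12-month-lag analyses. ITT keeps early stoppers, as-treated drops them at day 180, and the 12-month lag drops others. One index-date matching cannot equal all three analysed sets. Table 16 lists no balance check at day 180.

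**7. How large an imbalance could be.** Let a covariate have prevalence p in both arms at index, and let retention to day 180 be r₁ in covariate-positive empagliflozin users and r₀ in everyone else. Then p₁ = p·r₁ / [p·r₁ + (1 − p)·r₀], p₀ = p, and the standardized difference is (p₁ − p₀) / √{[p₁(1 − p₁) + p₀(1 − p₀)]/2}. The retention values are assumptions.

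| p | r₀ | r₁ | p₁ | Std. difference |
|---|---|---|---|---|
| 20% | 85% | 70% | 17.1% | −7.5% |
| 20% | 85% | 60% | 15.0% | −13% |
| 30% | 80% | 70% | 27.3% | −6.0% |
| 30% | 80% | 65% | 25.8% | −9.3% |
| 30% | 80% | 60% | 24.3% | −12.8% |

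Equal retention, or the same covariate effect in both arms, gives 0%. In the first pair, 10% is reached at about 34–35% stopping in covariate-positive empagliflozin users against 15% in every other group. If the covariate tripled cancer risk (assumed), the first two rows would multiply an unadjusted HR by (1 + 2 × 0.171)/(1 + 2 × 0.20) = 0.96 and (1 + 2 × 0.15)/1.4 = 0.93.

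**The case against.** The strongest reply is that no sentence puts the exclusion after matching. Table 6 describes patients eligible for the study population and stops at 30 June, which suggests that a cap was intended. This stands: a reader might infer that the plan prescribes a wrong order, but for late initiators it prescribes none.

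A reader might also infer that the Annex III date would remove a UK year. The main text runs to 2021 for CPRD, and Annex III Tables 17, 18, 37 and 38 have a 2021 row, so the date looks like a leftover that needs correcting.

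Protocol 8.1 mentions side effects as a reason for changing treatment, which might be read as evidence of differential stopping. It describes patients moving to empagliflozin before index. The documents give no data on early stopping by arm.

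Dropping short users is disclosed and intended (Protocol 8.3.1 and 8.9). The lag applies to both arms and credits neither with immortal time. Measuring covariates at index is not an error. The adjusted model already considers urinary tract infection, stones and HbA1c whatever their balance, and ITT keeps early stoppers. SAP 6.5.2 allows the time window to be relaxed. No stratification of the Cox model on matched sets is stated, so a patient whose partner is lost still counts.

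All of this reduces the size of the issue without closing it. Table 16 lists ITT for all urinary tract cancers only, not for bladder or renal cancer separately. The adjusted model's candidates are a short list. Nothing planned would show whether the as-treated arms are balanced at day 180.

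**Conclusion.** The point holds as an unspecified step and a missing check.

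**Late initiators.** The place of the 180-day rule is not stated and the index windows conflict. Read literally, the main text matches patients who cannot contribute: about 15% of Swedish and 13% of Finnish empagliflozin initiators, if the second half of 2020 equalled the first. The effect on total person-time is small, well under 1% in the Swedish calculation. No UK share is given, because Table 6 has no count for the second half of 2021.

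**Balance.** For the as-treated analysis, the patients whose balance is checked cannot be the patients analysed, so SAP 6.3's description of study entry does not fit the analysed set. Whether this produces imbalance, and in which direction, is unknown. Passing 10% needs fairly strong early stopping confined to one arm and tied to the covariate. A claim that the hazard ratios will be biased would go beyond the documents. The case for the check is that it is nearly free.

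**What to change.** 1. Set one last index date per country at study end minus 180 days: 4 July 2020 for Sweden and Finland, 4 July 2021 for CPRD. State it in SAP 4.2.2, 5.1.2 and Table 2, apply it before propensity estimation and matching, and correct the Annex III definition to agree. No analysable person-time is lost, because the patients removed contribute none.
2. Add a table of standardized differences of index-date covariates among matched patients at risk on day 180 of the as-treated analysis. Adjust the as-treated base model also for covariates at or above 10% in that table. This costs one table per country and possibly one or two more covariates. The as-treated and ITT adjustment sets may then differ, which should be stated.
3. Report the number of matched patients lost before day 180 by arm and reason (stop or switch, death, cancer, emigration or transfer, other), as an extra step in the flowchart.

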8.9 LIMITATIONS OF THE RESEARCH METHODS

There are several methodological challenges to conducting epidemiological studies evaluating the comparative safety of glucose lowering medications [P12-13528, P14-17457, R14-4378, R13-1120, R10-6638].

The last (fifth) interim report (ANNEX 1) presented sample sizes of the study populations. It was noted that SGLT-2 inhibitor users were few and so that group was removed from analyses as stated in the amendments and updates, [Section 4](#).

The actual use of prescribed or purchased drugs, especially oral glucose lowering medications cannot be verified with certainty. Drug exposure will be defined by algorithmic approaches based on the amount dispensed/prescribed in a prescription. This may be subject to misclassification. Sensitivity analyses will be performed to assess the impact of the exposure definitions on the main results.

The time-dependent nature of the exposure also creates a challenge due to time-dependent confounding. Although PS matching is used to control for imbalances between exposed and unexposed cohorts at the time of index date, other factors potentially associated with both exposure and outcome after index date are not controlled by PS matching. This may be tackled by use of causal models (e.g., marginal structural models, inverse-probability of weighting approach) as sensitivity analysis.

The AT approach used as the primary analysis may result in exclusion of cancer cases due to censoring at treatment discontinuation of the index drug. This will be addressed in sensitivity analyses as an ITT approach will be conducted. The ITT approach is conservative and is subject to exposure misclassification, but it ensures the evaluation of all cases occurring during the study period. For this reason, we will conduct sensitivity analyses considering a longer time period after treatment discontinuation. Finally, we will apply a 6-month lag

period after the index date to the follow-up time in both the AT and ITT analyses to exclude subjects with only a short exposure time.

Determining the appropriate induction/promotion time window is challenging and typically only empirically based. Sensitivity analyses will evaluate a longer latency time window (12 months).

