Emigration from the study country	Censoring of follow-up time occurs at the date of emigration from the study country. Applied in all analyses.	UK: CPRD-GOLD and Aurum Sweden: Total population register ¹ Finland: Population register centre
Patient transfer	Censoring of follow-up time occurs at the date of patient transfer. Applied in all analyses.	UK: CPRD-GOLD and Aurum Sweden: NA Finland: NA
Incidence of any cancer during follow-up	A registered diagnosis of any cancer (excluding non-melanoma skin cancer) during follow-up. (ICD-10, ICD-7, ICD-O-3 and READ diagnosis codes in Annex I) Applied in all analyses.	UK: CPRD-GOLD and Aurum Sweden: Swedish cancer registry (SCR) Finland: FCR
Diabetes diagnosis other than type 2	A diagnosis of type 1 diabetes or other non-type 2 diabetes during follow-up identified using the same algorithm as used for the exclusion criteria (Section 4.2.4) Relevant ICD-10 codes and READ diagnosis codes are provided in Annex I. Applied in all analyses.	UK: CPRD and Aurum Sweden: NDR, NPR Finland: reimbursement registry
End of study period	Censoring of follow-up time occurs at end of study date i.e. 31 December 2020 (2021 for UK-CPRD). Applied in all analyses.	NA

Proprietary confidential information © 2024 Boehringer Ingelheim International GmbH or one or more of its affiliated companies

Treatment discontinuation (AT exposure- main analysis)	Censoring of follow-up time occurs 90 days after 
 - last day of medication (i.e. stop date) - new prescription of the other study drug or of a SGLT-2 inhibitor Applied only in analyses using the AT exposure definition.	UK: CPRD-GOLD and Aurum Sweden: SPDR Finland: FPR
Treatment discontinuation (AT exposure- sensitivity analysis)	Censoring of follow-up time occurs 180 days after 
 - last day of medication (i.e. stop date) - new prescription of the other study drug or of a SGLT-2 inhibitor Applied only in the sensitivity analysis using the AT exposure definition.	UK: CPRD-GOLD and Aurum Sweden: SPDR Finland: FPR

¹ The National patient register will be used if data on immigration/emigration are unavailable from the Total population register.

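### As-treated entry at day 180 is tested on follow-up that already includes the post-discontinuation tail, so patients off the index drug can enter; with the 180-day tail, discontinuation excludes nobody

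*SAP*

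**What the plan says.** SAP 5.1.3 sets the lag: "a latency period of 6 months (180 days) after the index date is applied". The entry rule follows: "Patients with less than 6 months (180 days) of follow-up time will be excluded". For the AT analysis, "the time at risk will begin after the latency period and end at urinary tract (bladder, renal or other) cancer" or at a censoring event, one of which is treatment discontinuation.

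The end of AT follow-up is fixed in two places. For the main analysis, SAP Table 4 says "Censoring of follow-up time occurs 90 days after" the last day of medication or a new prescription of the other study drug or an SGLT-2 inhibitor. For the sensitivity analysis it says "Censoring of follow-up time occurs 180 days after" the same events. SAP 5.1.6 agrees on the main rule: "The discontinuation date is defined as the stop date/start date of a new drug plus 90 days". Protocol 8.3.4 and 8.3.5 are built the same way.

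Two protocol statements describe the intended AT cohort. Section 8.3.1 defines AT exposure as ongoing use from 6 months after index. Citing typical prescription lengths of one month (UK) and three months (Sweden, Finland), it says "multiple prescriptions are required for a patient to have continuous ongoing treatment at 6 months after index date", so that one-prescription patients are unlikely to contribute. Section 8.9 says the 6-month lag is applied "in both the AT and ITT analyses to exclude subjects with only a short exposure time".

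**The concern.** The quantity compared with 180 days is follow-up time, and by Table 4 that time already contains the tail. No sentence in either document asks whether the patient is still taking the index drug at day 180. A patient can therefore stop or switch before day 180, be carried past it by the tail, and contribute only off-drug time to the arm assigned at index.

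Two things are at stake. First, the AT cohort does not have the property that protocol 8.3.1 and 8.9 claim for it. Second, the 180-day-tail analysis is presented as a change of tail length only (protocol 8.3.4), yet it also admits early stoppers and switchers whom the primary analysis excludes. If its hazard ratio differs from the primary one, the reader cannot tell which change is responsible.

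**Working it through.** The plan gives no figure to reproduce here. The statement that can be checked is the one in protocol 8.3.1 that multiple prescriptions are needed.

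**Inputs.** Lag 180 days; tail 90 days (main) or 180 days (sensitivity); gap of up to 30 days allowed (SAP 5.1.6); prescriptions of about 30 days (UK) and 90 days (Sweden, Finland) from protocol 8.3.1.

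**Rule.** Follow-up = stop (or switch) day + tail. The patient stays in if this is at least 180. Days at risk = stop day + tail − 180. The earliest stop day that passes is 180 − tail: day 180 with no tail, day 90 with the 90-day tail, day 0 with the 180-day tail.

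**One prescription only.**

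| Supply | Tail | Follow-up | Result |
|---|---|---|---|
| 30 days | 90 | 120 | excluded |
| 30 days | 180 | 210 | 30 days at risk, starting 150 days after stopping |
| 90 days | 90 | 180 | not excluded, 0 days at risk |
| 90 days | 180 | 270 | 90 days at risk, starting 90 days after stopping |

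**Primary analysis.** Stop or switch days 91-179 give 1-89 days at risk, all off the index drug or after the switch. The minimum number of prescriptions matches the protocol's premise only if drug time itself is tested: with no tail, UK patients need 6 prescriptions without gaps (6 × 30 = 180) or 4 with 30-day gaps (4 × 30 + 3 × 30 = 210), and Nordic patients need 2.

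**Switchers.** Exposure is fixed at index (SAP Table 5). With the 180-day tail, a DPP-4 initiator who starts empagliflozin on day 20 is followed to day 200. That patient adds 20 days to the DPP-4 arm, beginning 160 days after starting empagliflozin.

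**Size.** The documents give no persistence figures, so these are illustrations. Assume a constant stopping hazard, with S(t) the proportion still on drug. The share of entrants off drug at day 180 is [S(180 − tail) − S(180)] / S(180 − tail).

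- 20% off drug by day 180: S(90) = √0.8 = 0.894, so (0.894 − 0.800)/0.894 = 10.6% with the 90-day tail; (1 − 0.8)/1 = 20% with the 180-day tail.
- 40% off drug by day 180: S(90) = √0.6 = 0.775, giving 22.5% and 40%.
- Their person-time share is the integral of S(t − tail) − S(180) over days 180 to 180 + tail, divided by the integral of S(t − tail) from day 180 to the horizon. With a 1,000-day horizon this is 0.9% and 3.1% (90-day tail), and 3.4% and 10.4% (180-day tail).
- With 12-month persistence of 80% down to 50% and 876 days (2.4 years) instead, entrants off drug are 5.4-15.7% and 10.4-29.0%; person-time shares are 0.4-1.8% and 1.6-6.4%.

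**Allowing for 90-day supplies.** With exact 90-day fills and gaps of at most 30 days, one fill ends on day 90 and two end on days 180-210, so no Nordic stop date falls on days 91-179; only switches can. Stopping is then a UK matter in the primary analysis. From the expected counts and matching ratios in the protocol abstract and 8.5, the UK contributes 16,887 × 4 = 67,548 of 67,548 + 32,334 × 2 + 18,269 × 3 = 187,023 matched patients, or 36%. Scaling by 0.36, with equal follow-up assumed, gives about 4-8% of entrants (0.36 × 10.6 to 0.36 × 22.5) and 0.3-1.1% of person-time (0.36 × 0.9 to 0.36 × 3.1).

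**The case against.** The case against has four parts.

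*Order of operations.* The SAP does not say in words that the tail is added before the 180-day test, and I could not see Figure 1 of either document. Protocol 8.3.1, with its reference to ongoing use, might be read as requiring use at day 180. But the result does not turn on this order: even if the exclusion meant database follow-up, AT time at risk still runs from day 180 to stop plus tail, so the same patients are in it. The wording of 8.3.1 is the other side of the conflict, not an operational rule.

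*One-prescription users in the primary analysis.* A reader might infer that a single three-month Nordic dispensing enters the primary risk set. On the documents' own supply length it contributes zero days; only an assumed longer supply adds any (100 days would add 10). The protocol's word is also unlikely, not never. For the primary analysis this objection stands.

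*Purpose of the sensitivity analysis.* Protocol 8.9 presents a longer post-discontinuation period as a response to cancer cases lost by AT censoring, so recovering events after early stopping fits that aim. No section promises a fixed cohort, the 12-month lag also changes the cohort, and SAP Table 16 runs the analysis for urinary tract cancer only. This limits the consequence. It does not remove the mixing of two changes.

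*Purpose of the lag.* It is tempting to say the lag was meant to remove patients who stopped because of symptoms of an undiagnosed cancer. The documents give its purpose as an induction/promotion period, and assign diagnostic delay to the tail. That argument is not available here. The tail itself is deliberate and is not in question.

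**Conclusion.** The conflict is real, and the protocol shares it with the SAP. Patients who stopped or switched before day 180 can enter the AT risk set without being on the index drug, against protocol 8.3.1 and 8.9. For ITT the statement in 8.9 is simply wrong: discontinuation does not end ITT follow-up, so the lag cannot remove short users.

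In the primary analysis the effect is confined to stops and switches on days 91-179 and amounts to roughly 0.3-3% of person-time under the assumptions above. A reader might quote 11-23% of entrants. That range needs a smooth stopping curve in all three countries, which ignores 90-day supplies, and it counts heads rather than time at risk. The primary hazard ratio is unlikely to move much.

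The 180-day-tail analysis is where the point bites. Stop plus 180 always reaches day 180, so discontinuation excludes nobody, and one-prescription users and early switchers all enter. A difference from the primary result then cannot be attributed to tail length alone. The analysis still has some value for its stated aim of recovering lost cases. The day arithmetic needs no assumption; only the percentages do.

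**What to change.** In SAP 5.1.3, apply the entry test to treatment: a patient enters the AT risk set only if the stop or switch date, before any tail is added, is on or after day 180 (day 365 for the 12-month lag). Add the 90- or 180-day tail afterwards, and use this same AT cohort for both. At the least, hold the primary AT cohort fixed in the 180-day-tail analysis. Align protocol 8.3.5, and correct protocol 8.9 so that it no longer says the lag removes short users from the ITT analysis. If the sponsor prefers to let the tail count towards entry, say so and withdraw the statements in 8.3.1 and 8.9 that imply otherwise.

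The work is a few sentences and one date comparison in the code. The cost is the small off-drug person-time above, plus any delayed-diagnosis events in patients who stopped or switched on days 91-179. For example, a patient treated for 170 days and diagnosed on day 200 would drop out of AT, while one treated for 181 days and diagnosed the same day would count. Such events remain in the ITT analysis, which SAP Table 16 lists for urinary tract cancer as a whole. Because outcomes are rare, report how many are lost.
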